10. ADVERSE EVENTS

10.1. Definitions

10.1.1. Adverse events (AE)

- An adverse event (AE) is any untoward medical occurrence in a patient that develops or worsens in severity during the conduct of a clinical study of a pharmaceutical product and does not necessarily have a causal relationship to the study drug. An adverse event can, therefore, be any unfavorable and unintended physical sign, symptom, or laboratory parameter that develops or worsens in severity during the course of the study, or significant worsening of the disease under study (or any concurrent disease), whether or not considered related to the study drug. Accordingly, an adverse event could include any of the following:
- intercurrent illnesses
- physical injuries
- events possibly related to concomitant medication
- significant worsening (change in nature, severity, or frequency) of the disease under study or other pre-existing conditions. (NOTE: A condition, recorded as pre-existing, that is intermittently symptomatic [e.g., headache] and which occurs during the study should be recorded as an adverse event.)
- drug interactions
- events occurring during diagnostic procedures or any washout phase of the study
- laboratory or diagnostic test abnormalities occurring after the start of the study (i.e., after screening and once confirmed by repeat testing) that results in the withdrawal of the patient from the study, requires medical treatment or further diagnostic work-up, or is considered by the study investigator to be clinically significant. NOTE: Abnormal laboratory test results at the screening visit that preclude a patient from entering the study or receiving study treatment are not considered adverse events, but will be recorded to monitor data from patients who do not meet screening criteria.

Worsening of any of the Target or Non-Target Wart assessments should be reported as an AE ONLY if the use of the study medication is interrupted or discontinued or if therapy is required to manage the event.

The investigator must, for any Target or Non-Target Wart related AE, question the subject in detail to determine if there are any confounding factors (*e.g.*, irritation by clothing or activity, sunburn) for any such AE.

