12.2. Statistical Analysis of Efficacy

Primary and secondary efficacy analyses will be performed on the Per-Protocol population, defined as all randomized subjects who missed no more than 3 treatment visits, completed Visit 10 (primary analysis) and Visit 13 (secondary analysis), and who have not had a major protocol violation over that time period, including the use of a clinically relevant quantity of a prohibited medication as determined by the study Medical Monitor. No missing data imputation will be used for these analyses.

Visit 10 is considered to be the primary efficacy endpoint. In addition, some analyses will also be conducted at earlier and subsequent visits, and treated as exploratory analyses. Some sensitivity efficacy analyses may also be re-performed on the Intent to Treat population, defined as those randomized subjects who have at least one post-baseline visit with required efficacy data collection and who completed Visit 10 with required collection of efficacy data. For those analyses, missing efficacy data for intermediate visits will be imputed using the last observation carried forward (LOCF) procedure. A determination as to the performance of analyses using the Intent to Treat population will be based on the number and pattern of visits missed by randomized subjects. Exploratory analyses using models specified below may also be performed for separate age groups, depending on enrollment outcomes.

For all analyses, two-tail alpha will be set to 0.05 with no adjustment for multiple comparisons. ANOVAs and ANCOVAs will include Site in the model only if doing so improves the sensitivity of the model for comparing treatment groups.

After the last randomized subject has completed Visit 10 the database will be validated, locked through Visit 10 and unblinded for the purpose of analyzing efficacy data through Visit 10. Those analyses are not considered to be interim analyses as the results will be final. Data will continue to be collected through Visit 13 for all subjects, and the full database will subsequently be locked for efficacy analysis (including durability of response) beyond Visit 10, and for the analysis of safety and all other clinical data.

The primary efficacy analysis will be a comparison between treatment groups based on the mean change in Target Wart PWA from Baseline (Visit 2) to Visit 10, using Analysis of Covariance with Baseline PWA as the covariate.

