9. STATISTICAL ANALYSIS METHODS

9.1. Statistical Analysis of Efficacy Data

Primary and secondary efficacy analyses will be performed on the Per-Protocol population, defined as all randomized subjects who missed no more than 3 treatment visits, completed Visit 10 (and Visit 13 for purposes of the Visit 13 analysis), and who have not had a major protocol violation over that time period including the use of a clinically relevant quantity of a prohibited medication as determined by the study Medical Monitor. No missing data imputation will be used for these analyses.

Visit 10 is considered to be the primary efficacy endpoint. In addition, some analyses will also be conducted at earlier and subsequent visits, and treated as exploratory analyses. Some sensitivity efficacy analyses may also be re-performed on the Intent to Treat population, defined as those randomized subjects who have at least one post-baseline visit with required efficacy data collection and who completed Visit 10 with required collection of efficacy data. For those analyses, missing efficacy data for intermediate visits may be imputed using the last observation carried forward (LOCF) procedure. A determination as to the performance of such analyses using the Intent to Treat population will be based on the number and pattern of visits missed by randomized subjects. Exploratory analyses using models specified below may also be performed for separate sub-groups, depending on enrollment outcomes.

For all analyses, two-tail alpha will be set to 0.05 unless otherwise specified, with no adjustment for multiple comparisons. ANOVAs and ANCOVAs will include Site in the model only if doing so improves the sensitivity of the model for comparing treatment groups.

After the last randomized subject has completed Visit 10 the efficacy data captured to date in the database will be validated, locked through Visit 10 and unblinded for the purpose of analyzing efficacy data through Visit 10. Those analyses are not considered to be interim analyses as the results will be final. Data will continue to be collected through Visit 13 for all subjects, and the full database will subsequently be locked for efficacy analysis (including durability of response) beyond Visit 10, and for the analysis of safety and all other clinical data.

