The primary efficacy analysis will be a comparison between treatment groups based on the mean change in Target Wart PWA from Baseline (Visit 2) to Visit 10, using Analysis of Covariance with Baseline PWA as the covariate.

Secondary efficacy analyses will include comparisons between treatment groups based on the following: the proportion of subjects with the Target Wart Clear (PWA = 0) at Visit 10 using a one-tail Fisher's Exact Test; the proportion of subjects with the Target Wart Clear or Near-Clear (PWA = 0 or 1) at Visit 10 using a one-tail Fisher's Exact Test; the proportion of subjects with all treated warts Clear at Visit 10 using a Cochran-Mantel-Haenszel test stratified by number of treated warts; the proportion of subjects with all treated warts Clear or Near-Clear at Visit 10 using a Cochran-Mantel-Haenszel test stratified by number of treated warts; the proportion of subjects with all treated warts Clear or Near-Clear at Visit 10 using a Cochran-Mantel-Haenszel test stratified by number of treated warts; the mean of persubject percentages of treated warts that are Clear at Visit 10 using Analysis of Variance; the

mean of per-subject percentages of treated warts that are Clear or Near-Clear at Visit 10 using Analysis of Variance; and the mean of per-subject percent change from baseline PWA for treated warts using Analysis of Variance.

Durability of response in the Active treatment group will be evaluated by calculating the proportion of those treated warts achieving a PWA status of Clear at Visit 10 which continue to maintain a PWA status of Clear at Visit 13. This analysis will be performed separately for Target Warts, and for all treated warts. The 95% confidence limits around the calculated proportions will also be calculated in order to estimate the population lower limit value of the observed sample proportions.

Exploratory analyses may be conducted using a subset of the above analysis models, based on lesion sub-groups including body location, age, time to clearance, and also the following baseline wart classification: warts that are determined to be treatment-naive vs. recalcitrant.

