11. TABLES AND LISTINGS: TITLES

Note: Mock tables and listings are provided in a separate document. They are intended to illustrate the format, layout and content of each table and listing. Final tables and listings may differ as appropriate. The mock tables and listings may include data from a previous study but will be superseded by data from the present study. Study identifier will be changed to A-101-WART-202. Treatment groups will be changed to A-101 Solution 45% and A-101 Solution Vehicle. Table numbers may be re-defined by the Medical Writer. Titles and Footnotes will be modified as required.

DEMOGRAPHIC DATA SUMMARY TABLES

Table 14.1.1	Disposition of Randomized Subjects – Study Completion/Subject
	Accountability
Table 14.1.2	Summary of Demographics – Randomized Population (Intent-to-Treat)
Table 14.1.3	Summary of Demographics – Safety Population
m 11 4444	

- Table 14.1.4
 Summary of Demographics Per Protocol Population
- Table 14.1.5
 Protocol Violations Randomized Subjects

EFFICACY DATA SUMMARY TABLES

Table 14.2.1	Target Wart Assessments: PWA Mean and Mean Change from Baseline, by Treatment and Visit – PP Population
Table 14.2.2	Target Wart Assessments: N and % PWA Responders with PWA Clear $(PWA = 0)$, by Treatment and Visit – PP Population
Table 14.2.3	Target Wart Assessments: N and % PWA Responders with PWA Clear or Near-Clear (PWA = 0 or 1), by Treatment and Visit – PP Population
Table 14.2.4	Treated Wart Assessments: N and % PWA Responders with All Treated Warts Clear (PWA = 0), Stratified by Number of Treated Warts, by Treatment and Visit – PP Population
Table 14.2.5	Treated Wart Assessments: N and % PWA Responders with All Treated Warts Clear or Near-Clear (PWA = 0 or 1), Stratified by Number of Treated Warts, by Treatment and Visit – PP Population
Table 14.2.6	Treated Wart Assessments: Mean of Per-Subject % of Treated Warts Clear $(PWA = 0)$, by Treatment and Visit – PP Population
Table 14.2.7	Treated Wart Assessments: Mean of Per-Subject % Change from Baseline PWA for Treated Warts, by Treatment and Visit – PP Population
Table 14.2.8	Durability of Response: N and % of Visit 10 Responders (PWA = 0) with $PWA = 0$ at Visit 13, by Active Treatment – PP Population
Table 14.2.9	Target Wart Assessments: PWA Frequency Distributions, by Treatment and Visit – PP Population
Table 14.2.10	Treated Wart Assessments: PWA Frequency Distributions, by Treatment and Visit – PP Population

Page 28 of 32 Date: 21 November 2017

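### Durability is computed on the Visit 13 Per-Protocol set, with no rule for a cleared wart that returns and is treated outside the study; the lost response can drop out of the denominator or count as maintained

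*SAP*

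**What the plan says.** **Measure.** SAP 9.1 and Protocol 12.2 define durability, in the active arm only and with Visit 13 as the later visit, by this share: "proportion of those treated warts achieving a PWA status of Clear at Visit 10 which continue to maintain a PWA status of Clear". It is done separately for Target Warts and for all treated warts. SAP 9.1 adds an interval: "The 95% confidence limits around the calculated proportions will also be calculated in order to estimate the population lower limit value". No interval method is named.

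**Analysis set.** The only durability table, Table 14.2.8 in SAP 11, opens its title with "Durability of Response: N and % of Visit 10 Responders (PWA = 0) with". It then asks for a grade of 0 again at the later visit, and the title ends "Visit 13, by Active Treatment – PP Population".

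**Per-Protocol definition.** Protocol 12.2 requires subjects who "completed Visit 10 (primary analysis) and Visit 13 (secondary analysis), and who have not had a major protocol violation over that time period". SAP 9.1 has the same structure and also counts as a major violation "including the use of a clinically relevant quantity of a prohibited medication as determined by the study Medical Monitor". Neither section uses imputation. SAP 7.3.1 is worded differently. It ties the absence of a major violation to completing Visit 10, and for the Visit 13 analysis adds only that the subject had a Visit 13.

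**Wart treatment after Visit 10.** Study drug is not given at Visits 10 to 13. Protocol 7.8.3 prohibits a list of wart therapies during the study, including liquid nitrogen, imiquimod and over-the-counter products. Protocol 5.3 lists prohibited medication, through Visit 13, among the reasons why a subject may be removed. Protocol 10.1.1 allows that a worsened wart may need treatment: worsening is reported as an adverse event "ONLY if the use of the study medication is interrupted or discontinued or if therapy is required to manage the event".

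**Sensitivity analysis.** SAP 9.1 says that Intent-to-Treat analyses may be run, and that the decision on "using the Intent to Treat population will be based on the number and pattern of visits missed by randomized subjects".

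**The concern.** Treatment of a returned wart is a consequence of losing the response. If it removes the subject from the analysis set, exclusion depends on the outcome being measured. If the subject is kept and the outside therapy clears the wart by Visit 13, a failure of durability is recorded as a success. Neither document says that use of another wart therapy counts as loss of response.

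Duration of response in all treated warts is a stated secondary objective, and this is the only analysis specified for it. The stated purpose of the interval is a lower limit for the population, so an upward shift affects the figure a reader is most likely to rely on. The harm would be an over-favourable durability statement. No hypothesis test is affected.

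**Working it through.** **Step 1. What happens to a re-treated relapse.** Take a wart that is Clear at Visit 10, returns, and is treated with a prohibited therapy before Visit 13.

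- *Judged clinically relevant:* under SAP 9.1 and Protocol 12.2 the subject is excluded, with every cleared wart that subject has. Under the narrower reading of SAP 7.3.1, a subject who attends Visit 13 stays in.
- *Removed before Visit 13:* excluded under either reading.
- *Retained and Clear at Visit 13:* counts as maintained, because Table 14.2.8 uses only Visits 10 and 13.
- *Retained and not Clear at Visit 13:* counts as lost, which is correct.

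The gap is therefore limited to relapses that are re-treated or whose subjects are removed. An untreated relapse still visible at Visit 13 is counted properly.

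**Step 2. Target Warts.** The documents give no clearance, relapse or re-treatment rates, so every count here is an assumption. Let n warts be Clear at Visit 10 and r be truly maintained. Excluding j re-treated relapsers gives r/(n − j). Counting j as maintained gives (r + j)/n. Lower limits are exact (Clopper-Pearson, two-sided 95%).

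| Assumed case | Proportion | Lower limit |
|---|---|---|
| n = 20, 5 relapse, all counted as lost | 15/20 = 75% | 51% |
| 1 re-treated relapser excluded | 15/19 = 79% | 54% |
| 2 excluded | 15/18 = 83% | 59% |
| 3 excluded | 15/17 = 88% | 64% |
| 1 counted as maintained | 16/20 = 80% | 56% |
| 2 counted as maintained | 17/20 = 85% | 62% |
| No re-treatment (j = 0) | 15/20 = 75% | 51% |

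With 12 cleared and 3 relapsing, 9/12 = 75% (43%) becomes 9/10 = 90% (56%) with two excluded, or 11/12 = 92% (62%) with two counted as maintained.

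**Step 3. The opposite direction.** Exclusion is by subject. If only a Non-Target Wart, or a wart never cleared, is treated while the Target Wart stays Clear, exclusion removes a maintained Target Wart: 15/20 = 75% becomes 14/19 = 74%.

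**Step 4. All treated warts.** Start from an assumed 30/40 = 75% and exclude one subject with one relapsed wart. With 0, 1 or 3 other maintained warts the result is 30/39 = 77%, 29/38 = 76% or 27/36 = 75%. The shift is small, and upward only when the subject's own maintained share is below the overall proportion.

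**Step 5. Missing Visit 13.** Suppose 1 relapser and 2 durable warts of the 20 lack Visit 13. Observed cases give 13/17 = 76%. Counting the missing as not maintained gives 13/20 = 65%, and as maintained 16/20 = 80%. The plan would show only the first.

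**Step 6. Several warts per subject.** This concerns all treated warts only. A simulation assumed 60 active subjects with 1 to 4 warts, 10–50% clearance, 65–85% durability and within-subject correlation (ICC) of 0 to 0.7.

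- At ICC 0.3–0.7 and 30–50% clearance, an exact interval that ignores clustering covered 86.0–96.6%. Its lower limit exceeded the truth in 1.5–6.9% of trials (nominal 2.5%).
- At ICC 0–0.1 it covered 95–99%.
- In the first of these settings, a subject-clustered t interval had its lower limit too high in 3.8–10.6% of trials. A bootstrap of subjects, run in fewer settings, had 4.1–6.8%.
- Exact limits that use the number of subjects with a cleared wart as the sample size had 0.4–2.1%.

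**The case against.** **The violation window is not certain.** Under SAP 7.3.1 a subject who uses a prohibited therapy after Visit 10 but attends Visit 13 may stay in the set. This stands: exclusion for use alone depends on the SAP 9.1 and Protocol 12.2 wording. Under the narrower reading the subject is retained, so a re-treated wart that is Clear at Visit 13 still counts as maintained.

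**Continued maintenance might mean Clear throughout.** PWA is scored at Visits 11 and 12, so a relapse seen then could be treated as a failure. The text allows this reading but does not state it, and the table title names only Visits 10 and 13. It would also not return an excluded subject to the denominator.

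**Evidence that re-treatment will occur is thin.** Protocol 10.1.1 is an adverse event reporting rule, Protocol 5.3 is permissive, and SAP 9.1 says that collection continues through Visit 13 for all subjects. This is fair, and it is why the size is conditional. Keeping a re-treated wart as maintained also requires the Medical Monitor to judge the use not clinically relevant, or the narrower reading, or a therapy off the prohibited list.

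**An Intent-to-Treat run or the listings would reveal it.** Neither Intent-to-Treat definition excludes violators, so such a run could restore a relapser who has a Visit 13 score. But it is optional, is triggered by missed visits, has no durability table, and would still count a re-treated Clear wart as maintained. Violations and medications are tabulated or listed, but no planned output recomputes durability.

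**Stronger readings to avoid.** A reader might infer that Target Wart durability is always overstated; step 3 shows that exclusion can lower it. A reader might also infer that the all-warts figure, the one named in the objective, is badly distorted; step 4 does not show that.

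**Conclusion.** The point holds as a gap in how durability is defined, and it should be fixed. The plan has no rule for outside treatment of a cleared wart that returns, and its two Per-Protocol definitions do not agree. When the re-treated wart is the Target Wart, exclusion and counting as maintained both raise the proportion and its lower limit. In the assumed example the rise is 8 to 10 percentage points for two re-treated relapsers (75% to 83% or 85%), and the lower limit moves from 51% to 59% or 62%. When only another wart is treated, exclusion can lower the Target Wart figure slightly. For all treated warts, one excluded subject moves the figure by 0 to 2 points.

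These sizes rest wholly on assumed counts, and with no re-treatment the effect is zero. The documents do not support saying that durability will be overstated, only that the plan permits it and would not show it. The analysis is descriptive and single-arm, so the primary comparison is untouched.

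The missing-visit and interval points are secondary. A missing Visit 13 has a rule (excluded, no imputation), though no bounds are shown. Clustering matters moderately at most, and little or not at all with low correlation, few warts per subject or low clearance.

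**What to change.** **Main change, in SAP 9.1, Protocol 12.2 and Table 14.2.8:**

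1. Reconcile the Visit 13 Per-Protocol definition in SAP 7.3.1 with that in SAP 9.1 and Protocol 12.2.
2. Use as denominator the active-arm treated warts Clear at Visit 10 in the Visit 10 Per-Protocol set. Apply no exclusion that arises after Visit 10. For Target Warts this matches the Visit 10 responders in Table 14.2.2.
3. Count a wart as not maintained if any non-study wart-directed therapy is used on it between Visit 10 and Visit 13, whether or not it is on the prohibited list. Protocol 2.1 names cantharidin, podophyllin and trichloroacetic acid as wart treatments, and Protocol 7.8.3 does not list them. This is an analysis rule only and does not bear on what care a subject may receive.
4. Record which wart was treated. Protocol 7.8.2 records the therapy but does not mention the wart.
5. State whether a PWA above 0 at Visit 11 or 12 counts as loss.
6. Show the planned Visit 13 Per-Protocol result as a sensitivity analysis.

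**Secondary:**

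- Show missing Visit 13 both ways (all maintained, all not maintained) beside observed cases.
- Use an exact binomial interval for Target Warts.
- For all treated warts, either use a conservative subject-based interval or label the interval as not adjusted for clustering. One such interval applies exact limits to the observed wart proportion, with the number of subjects having a cleared wart as the sample size. Since a lower limit is the aim, clustered-t or bootstrap limits are not an improvement here (step 6).

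**Cost.** Wording in two documents, minor reprogramming of one table and one added data item. The durability figure may be lower. The subject-based interval was 6–37% wider than the unadjusted exact one in the simulation, and is over-conservative if warts are nearly independent. Sample size and the primary analysis do not change.

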Page 45 of 53 Amendment 2 Version 3 Date: 05 December 2017 Secondary efficacy analyses will include comparisons between treatment groups based on the following: the proportion of subjects with the Target Wart Clear (PWA = 0) at Visit 10 using Fisher's Exact Test; the proportion of subjects with all treated warts Clear at Visit 10 using a Cochran-Mantel-Haenszel test stratified by number of treated warts; and the mean of per-subject percentages of treated warts that are clear at Visit 10 using Analysis of Variance. The number of treated warts Clear at Visit 10 will also be analyzed using a Cochran-Mantel-Haenszel test stratified by number of treated warts Clear at Visit 10 will also be analyzed using a Cochran-Mantel-Haenszel test stratified by number of treated warts.

Durability of response in the Active treatment group will be evaluated by calculating the proportion of those treated warts achieving a PWA status of Clear at Visit 10 which continue to maintain a PWA status of Clear at Visit 13. This analysis will be performed separately for Target Warts, and for all treated warts. The 95% confidence limits around the calculated proportions will also be calculated in order to estimate the population lower limit value of the observed sample proportions.

Exploratory analyses will be conducted using a subset of the above analysis models, based on the following baseline wart classifications: warts that are determined to be treatment-naive vs. recalcitrant.

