5.3. Physician's Wart Assessment (PWA)

The Physician's Wart Assessment (PWA) is the Investigator's assessment of the severity of each Target and Non-Target Wart at a particular time point. The Investigator should NOT refer to any other assessments to assist with this evaluation. This evaluation IS NOT a comparison with the PWA at any other visit.

At every study visit, the Investigator will assess the Target and Non-Target Warts and report the one integer that best describes the Target and Non-Target Wart severity using the following scale. At any visit where a study medication treatment is performed, the PWA must be completed prior to the treatment.

	Physician's Wart Assessment
Grade	Descriptor
0	Clear: No visible wart. No further treatment is indicated
1	Near Clear: A visible wart that is less than 3mm in maximal diameter (or length)
2	A visible wart \geq 3mm and <6 mm in maximal diameter (or length)
3	A visible wart \geq 6mm in maximal diameter (or length)

At Visit 1 for the subject to be enrolled and at Visit 2 for the subject to be randomized each Target and Non-Target Wart must have a PWA grade ≥ 2 .

At Visits 3-9, Target and Non-Target Warts must have a PWA > 0 to be retreated. If the Investigator cannot assess the PWA for a Target or Non-Target Wart (*e.g.*, the Target /Non-Target Wart cannot be visualized because of an LSR such as edema, scabbing, etc.) she/he must report the reason in the subject's CRFs. The Target/Non-Target Wart must not be retreated at that visit, and the subject should be seen at the next scheduled visit.

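### SAP 9.1 lists time to clearance, a post-randomisation outcome, among the sub-groups for rerunning the efficacy models; arm comparisons within its strata would remove or distort the treatment effect

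*SAP*

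**What the plan says.** The last paragraph of SAP 9.1 opens "Exploratory analyses may be conducted using a subset of the above analysis models" and continues "based on lesion sub-groups including body location, age, time to clearance, and also the following baseline wart classification", the classification being treatment-naive against recalcitrant warts. The models set out earlier in that section include the primary one, "mean change in Target Wart PWA from Baseline (Visit 2) to Visit 10, using Analysis of Covariance with Baseline PWA as the covariate", and secondary ones such as "the proportion of subjects with the Target Wart Clear (PWA = 0) at Visit 10 using a one-tail Fisher's Exact Test" and "the proportion of subjects with the Target Wart Clear or Near-Clear (PWA = 0 or 1) at Visit 10 using a one-tail Fisher's Exact Test". The others are Cochran-Mantel-Haenszel tests and analyses of variance on all treated warts.

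SAP 5.3 defines grade 0 as "Clear: No visible wart. No further treatment is indicated" and grade 1 as "Near Clear: A visible wart that is less than 3mm in maximal diameter (or length". It has PWA graded at every visit and requires grade 2 or more for each wart at Visit 2.

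Protocol 12.2 has a shorter exploratory list: "based on the following baseline wart classifications: warts that are determined to be treatment-naive vs. recalcitrant", plus age groups if enrolment allows. Time to clearance is not on it. The SAP gives no definition, cut-points or rule for never-cleared warts, and no table title in SAP 11 covers it.

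**The concern.** Body location, age and treatment history are fixed before the first application. Time to clearance is not. No wart is clear at Visit 2, so the variable comes into being only under treatment, and the scale that dates clearance also supplies the Visit 10 endpoints. Stratifying on it sorts warts by their response. The arms within a stratum are then no longer the groups that were randomised.

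A reader of such a table could take a null result in the cleared strata as evidence about the drug, or take the difference among uncleared warts as an effect in resistant warts. Neither reading would be sound. The strata are also undefined, and SAP 9.1 unblinds the efficacy data once Visit 10 is locked, so cut-points could be chosen with results in hand.

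**Working it through.** **The plan's own figures.** None is attached to this analysis. SAP 7.1 claims more than 90% power for the primary analysis but states no effect size or standard deviation, so it supplies no clearance rates. The rates used below are assumptions.

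**Step 1: what follows without simulation.** Let B be PWA at Visit 2 (2 or 3), Y the PWA at Visit 10, and T the first visit with PWA 0. Suppose clearance, once reached, lasts to Visit 10.

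- Cleared by Visit 10: Y = 0 for every wart. Target Wart Clear is 100% v 100%. The change is Y - B = -B, so the ANCOVA (change = a + b × arm + c × B) fits exactly with a = 0, b = 0, c = -1. The treatment estimate b is zero whatever the drug does.
- Not cleared by Visit 10: Y is 1, 2 or 3. Target Wart Clear is 0% v 0%. PWA change and Clear or Near-Clear can still differ between arms.

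**Step 2: size under assumed rates.** A simulation of the 0-3 scale over Visits 3 to 10 used 600,000 subjects per arm.

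- From the documents: the scale, the entry rule, the weekly visits, the ANCOVA, and about 120 evaluable subjects at 1:1, hence 120 / 2 = 60 per arm.
- Assumed: baseline 60% grade 2 and 40% grade 3; weekly chance of a one-grade improvement of 0.15 v 0.05, 0.20 v 0.08 or 0.30 v 0.15 (active v vehicle); weekly worsening of 0.02; weekly recurrence of a cleared wart of 0, 0.03 or 0.06.

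With no recurrence:

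| Weekly improvement | ANCOVA, overall | ANCOVA, first clear V3-6 | ANCOVA, first clear V7-10 | ANCOVA, uncleared by V10 | Clear or Near-Clear, overall | Clear or Near-Clear, uncleared |
|---|---|---|---|---|---|---|
| 0.15 v 0.05 | -0.713 | 0.000 | 0.000 | -0.405 | 53.0% v 20.0% | 38.7% v 17.2% |
| 0.20 v 0.08 | -0.788 | 0.000 | 0.000 | -0.391 | 65.2% v 30.9% | 45.8% v 24.8% |
| 0.30 v 0.15 | -0.777 | 0.000 | 0.000 | -0.324 | 82.7% v 52.8% | 56.8% v 38.6% |

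The uncleared stratum keeps 0.405/0.713 = 57%, 0.391/0.788 = 50% and 0.324/0.777 = 42% of the overall PWA difference. Its Clear or Near-Clear difference is 21.5, 21.0 and 18.2 points, against 33.0, 34.3 and 29.9 overall.

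**Step 3: where the treatment effect goes.** Expected numbers per 60 subjects, active v vehicle:

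| Weekly improvement | First clear V3-6 | First clear V7-10 | Uncleared by V10 |
|---|---|---|---|
| 0.15 v 0.05 | 4.1 v 0.5 | 9.9 v 1.5 | 46.1 v 58.0 |
| 0.20 v 0.08 | 7.0 v 1.3 | 14.5 v 3.6 | 38.6 v 55.2 |
| 0.30 v 0.15 | 14.1 v 4.1 | 21.8 v 9.8 | 24.1 v 46.1 |

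Much of the effect appears as stratum membership. The early stratum is small on vehicle, and nearly empty in the first two scenarios. The uncleared stratum compares different selected fractions of the two arms.

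**Step 4: relaxing persistence.** With weekly recurrence of 0.03 or 0.06, the early stratum is no longer fixed. Clear is 81-92% v 78-90% and the ANCOVA estimate is -0.02 to -0.05. The uncleared stratum stays within -0.32 to -0.41.

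**The case against.** The strongest reply is that the sentence need not mean a between-arm comparison. The paragraph before it describes durability in the active group, among warts already Clear at Visit 10, and the exploratory sentence allows any subset of the preceding analyses. Durability by time to clearance compares no arms and asks a sensible question: whether warts that clear early stay clear. That use is legitimate. But the sentence does not confine time to clearance to durability, and as worded it equally permits the ANCOVA and Fisher tests within these strata.

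It may also be a drafting slip for time to clearance as an outcome. The text does not say so, and none of the models listed handles warts that never clear.

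Two stronger readings are tempting and should be resisted.

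- A reader might infer that the treatment effect vanishes in every subgroup by construction. It does not. That is exact only for Target Wart Clear, and for PWA change in cleared strata, and only if clearance persists to Visit 10. The plan's own durability analysis allows for loss of clearance. Because the SAP sets no cut-off, a wart first clear at Visits 11 to 13 could fall in a cleared stratum without being clear at Visit 10. The per-subject endpoints on all treated warts are not fixed by one wart's clearance time.
- A reader might infer that the plan says nothing on whether active-treated warts clear sooner. Table 14.2.2 gives Target Wart Clear by treatment and visit, Tables 14.2.4, 14.2.6, 14.2.9 and 14.2.10 are also by visit, and SAP 9.1 foresees exploratory analyses at earlier visits. What is missing is a formal time-to-clearance comparison, which would supplement these tables.

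**Conclusion.** The point stands at low severity. As worded, SAP 9.1 permits arm comparisons conditioned on the response. They would return zero by definition for some endpoint and stratum combinations, and an attenuated, selected difference for others: about -0.3 to -0.4 grade among uncleared warts against -0.7 to -0.8 overall. Those sizes rest on assumed improvement, worsening and recurrence rates and say nothing about this trial's actual results. The loss of the randomised comparison does not depend on them; it follows from the entry rule and the shared scale.

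The analysis is exploratory, optional and without a listed table. No primary or secondary result uses it, and nothing here casts doubt on those results.

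**What to change.** Delete time to clearance from the sub-group list in SAP 9.1 and state that between-arm subgroup analyses use baseline characteristics only. Any use of it as a stratifier should be confined to the durability description within the active arm.

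If speed of clearance is of interest, add it as an exploratory outcome compared between arms: the first visit with Target Wart PWA = 0 over Visits 3 to 10, by a discrete-time model or Kaplan-Meier, with never-cleared warts censored at Visit 10. For all treated warts, treat the subject as the cluster. This would supplement the by-visit Clear tables.

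The cost is a change of SAP wording and one extra exploratory table. PWA is already graded at every visit, so no new data are needed.
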